4.4. Collection of data and variables to be studied

Anamnesis: Collection of clinical data in the medical history: history of obesity, evolution of weight, associated comorbidities, personal and family history. Dietary history.

Anthropometric data: Weight, size, waist circumference, BMI.

Electrogastrography data: clinical diagnosis, percentage distribution, ratios

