Variable weight loss and intolerance of BE procedures are appreciated. For this protocol we define Failure of BE methods when patient only obtain less than 25% of EWL after 6 months of BE, according to the Part 1 of the BAROS (Bariatric Analysis and Reporting Outcome System) scale adapted to endoscopic treatment (2) (Table 1).

After BIG placement, patients present intolerance such vomit and abdominal pain in 70-90% of cases at the first week but these effects can be extended up to three weeks (18%) and removal of the balloon in 4% of patients (3). Gastric emptying measured by gastric scintigraphy breath test or stable isotope breath tests show that there are physiological predictors of intolerance and response to BIG placement (10). Many studies show that patients after ESG at 6 months achieved a mean of 50% of EWL or more with rate of severe adverse events around 2% , including pain or nausea requiring hospitalization, upper gastrointestinal bleeding and peri-gastric leak or fluid collection (11).

After SEG.....

.....

Table 1 . BAROS (BARIATRIC ANALYSIS AND REPORTING OUTCOME SYSTEM) ADAPTED TO BARIATRIC ENDOSCOPY

1. Percentage of excess weight loss (%EWL): (Initial weight – Current weight) / (Initial weight – Ideal weight) × 100 (-1): Weight gain (0): Weight loss 0-24% (+1): Weight loss 25-49% (+2): Weight loss 50-74% (+3): Weight loss > 75%
 
2. Comorbidity: (-1): Aggravated (0): Unchanged (+1): Improved (unresolved) (+2): Improved: one major resolved, others improved (+3): Improved: all majors resolved, others improved
 
3. Quality of life questionnaire: (much worse, worse, unchanged, better, much better) Self-esteem (scale -1, -0.5, 0, +0.5, +1) Physical (scale -0.5, -0.25, 0, +0.25, +0.5) Social (scale -0.5, -0.25, 0, +0.25, +0.5) Work (scale -0.5, -0.25, 0, +0.25, +0.5) Sex (scale -0.5, -0.25, 0, +0.25, +0.5)
 
4. Complications: (-0.2): Per minor complication (-1): Per major complication (-1): In case of repeat endoscopy or surgery
	
Final score (sum total of above 4 items)
 
• No comorbidities: Failure: 0 or less Fair: 0-1.5 Good: 1.5-3 Very good: 3-4.5 Excellent: 4.5-6• Comorbidities: Failure: < 1 Fair: 1-3 Good: 3-5 Very good: 5-7 Excellent: 7-9
--	--

Thus, a fuller understanding of gastric physiology before undertaking BE treatments may lead to better patient selection for each procedure.

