Controversial findings on the correlation between EGG and GE have been reported in the literature. Different authors have said that a normal 3 cpm GMA may not predict normal GE and dysrhythmic GMA may be present in delayed GE but is also present in functional dyspepsia. Patients with delayed GE and abnormal EGG have more severe symptoms and more tachygastria in pre and post-prandial states than patients with normal GE. 80% of the non-obese population has normal EGG and 20% have variability (27, 28, 29, 30). There is only one preliminary study of GMA with WLST before BE techniques in obesity (31), but has not been studied in before and after BE procedures to determine subtypes of GMA and whether or not subtypes will predict successful bariatric outcomes.

Therefore, we propose a study to evaluate the GMA in response to the WLST in patients who have agreed to BE procedures. We hypothesize that GMA patterns in response to the WLST, the volume of water ingested and the array of symptoms elicited will help to predict successful outcomes of the bariatric procedures and thus help with patient selection for these procedures.

2.- WORKING HYPOTHESIS

Weight loss and long-term maintenance may be conditioned by changes in GMA, as well as by anatomical modifications induced by the bariatric procedure.

Since anatomical modifications of the stomach by the BE procedures are related to weight loss, our purpose is to determine whether different procedures to reduce gastric capacity will result in substantial changes in GMA and in the water load volume ingested. No studies that have studied obese population before and after such BE procedures are available.

Therefore, an important question is whether obese patients have the GMA that is similar to those with functional dyspepsia and normal weight (32). Also, the usefulness of electrogastrography as a new tool to customize choice of Bariatric therapies by determining success or failure based on GMA and WLST results has not been studied. GMA measures the normal or depleted gastric ICCs and the WLST measures gastric capacity, objective measures that may be important to predict success of Bariatric procedures and thus to help with patient selection to maximize efficacy and minimize side effects (32).

Hypothesis Question: Pre-intervention EGG can predict clinical success and adverse events after bariatric interventions?.

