Demonstrate the usefulness of EGG measuring the GMA by identifying subtypes with the Water Load Satiety Test (WLST) in obese adults to predict individual successful responses to BE treatments: Intra-gastric Balloon (IGB) placement and Apollo Endoscopic Sleeve Gastroplasty (ESG) method.

Demonstrate the usefulness of EGG measuring the GMA by identifying subtypes with the Water Load Satiety Test (WLST) in obese adults to predict individual successful responses to BE treatments: Intra-gastric Balloon (IGB) placement and Apollo Endoscopic Sleeve Gastroplasty (ESG) method

3.- OBJECTIVES

3.1.- Primary Objective –

- . Pre-intervention EGG parameters and/or changes in EGG parameters (one/three months) after bariatric intervention can predict clinical success at the end of follow up
- a. Pre-intervention EGG parameters and/or changes in EGG parameters after the bariatric intervention can predict adverse events at the end of follow-up.

3.2. Secondary:

- a. Secondary Objective
To predict suitable bariatric intervention for patients depending upon a pre-intervention EGG.
- b. EGG is a feasible diagnostic tool in obese population with reproducible and predictable results

4.- STUDY DESIGN AND METHODOLOGY

4.1. Type of study: Multicenter, prospective, observational study in patients with body mass index (BMI) at 30 kg/m² prior and after one, and three, six and 12 months of a bariatric procedure. All tests will be analyzed by one blinded specialist.

4.2. Study design: This is a pilot study, involving 2 hospitals in Spain and India, where 4 groups of patients will be recruited.

- a) Group of 50 patients who will undergo BIG placement
- b) Group of 50 patients who will undergo Endoscopic Sleeve Gastroplasty (ESG) Apollo method.
- c) Group of 50 patients who will undergo Surgical Sleeve Gastrectomy (SEG) Apollo method

d) Group of 50 patients who will undergo RYGB method

The protocol will be carried out in the run-up to the BE procedure until 12 months after of follow up. As a control group, 50 people (of the same age and gender) will be selected, with BMI less than 25% who voluntarily agree to participate in the protocol and have the same criteria of inclusion or exclusion of patients that belongs to all the groups, except BMI.

Duration – 18 months to 24 months

4.3. Characteristics of subjects:

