****The total volume of water consumed will be recorded.***

4.7. EGG signal analysis

EGG signal is reviewed for movement artifacts. Artifact – free minutes are chosen for blinded computer analysis (at baseline, three, six and 12 months recordings and for each type of BE procedure). The selected minutes of EGG are analyzed by spectral analysis

by computer applications. 3CPM EGGSAS GMAT Threshold software will be used for signal analysis. EGG data will be organized by clinical diagnosis. Water load volumes ingested that are <238 ml are considered abnormally low (33).

5.- STATISTIC

The normal distribution of the variables will be confirmed by the kolmogorov-Smirnoff test. Quantitative variables shall be expressed as mean s/e d or means (interquartile range). Comparison between groups will be performed by parametric or nonparametric tests, depending on the distribution of the variables. Spearman or Pearson correlation will be used for the study of correlations. The possibility of multivariate logistic regression analysis will be explored. An SPSS statistical programme will be used. EGG data will be descriptive in terms of overall clinical EGG diagnosis and normal or abnormal water load volume ingested. Symptom data before and after the WLST will be tabulated. These measures will be calculated before and 3 and 6 months after the BE procedures.

6.- STUDY LIMITATIONS

Recruitment of the number of subjects should not be a problem due to the high number of patients performed in the different centers and will allow the selection of those with the most approximate clinical results between groups.

A strength of the study is to have a control group of non-obese subjects, which will allow us to know the normal pattern of GMA in response to the WLST and whether it is similar to those worldwide reported in healthy individuals.

All tests will be carried out by the same expert operator in the medical center and analyzed by one specialist in EGG that received the blinded information from all the centers because it is a multicenter study, but the bariatric procedures will be performed by different operators from every center.

7.- STAGES OF DEVELOPMENT AND DISTRIBUTION OF THE AREAS OF ALL RESEARCH EQUIPMENT

The clinical study will be conducted simultaneously in AIG hospitals, Hyderabad, India, and Gastrodex, Dexeus University Hospital center in Spain. The task layout of the study team members will be as follows:

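### Adverse events are a primary outcome in objective 3.1(a), but the protocol text available neither defines them nor provides for collecting them

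*Protocol*

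**What the plan says.** **Adverse events as an outcome.** Protocol section 3.1(a) reads "Pre-intervention EGG parameters and/or changes in EGG parameters after the bariatric intervention can predict adverse events at the end of follow-up". The hypothesis question in section 2 is "Pre-intervention EGG can predict clinical success and adverse events after bariatric interventions", and the Summary carries the same hypothesis.

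**Data to be collected.** Section 4.4 gives three blocks:
- clinical history: "Collection of clinical data in the medical history: history of obesity, evolution of weight, associated comorbidities, personal and family history", plus dietary history;
- "Anthropometric data: Weight, size, waist circumference, BMI";
- "Electrogastrography data: clinical diagnosis, percentage distribution, ratios".

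Section 4.5 adds the volume of water drunk and visual analogue scores for fullness, hunger, nausea, bloating and abdominal discomfort. The scores are taken before the recording and at 10, 20 and 30 minutes after the water.

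**Data to be analysed.** Section 5 names the EGG diagnosis, normal or abnormal water volume, and symptoms around the water load test. It adds: "These measures will be calculated before and 3 and 6 months after the BE procedures".

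**Background.** Section 1.3 reports that after balloon placement "patients present intolerance such vomit and abdominal pain in 70-90% of cases at the first week", with effects lasting up to three weeks (18%) and balloon removal in 4%. It gives severe adverse events after endoscopic sleeve gastroplasty (ESG) as about 2%. Table 1, the adapted BAROS scale, has an item 4 that scores minor complications, major complications and repeat endoscopy or surgery. Section 1.3 uses only Part 1 of the scale, percentage excess weight loss (EWL), to define failure.

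**The concern.** The primary objective has two outcomes, and only one has a data source. Clinical success can be built from what is collected: weight is in section 4.4, and section 1.3 sets a failure threshold of less than 25% EWL at six months. Adverse events have no definition, grade, time window or method of collection in the text available.

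This cannot be left to a statistical analysis plan. Such a plan can say how events are analysed, but it cannot supply observations that sites were never asked to make. Early symptoms not recorded when they occur are hard to recover reliably later. The study compares four procedures at two hospitals. If each site records what it sees fit, differences in event status may partly reflect recording practice, and an association with EGG could not be read cleanly.

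**Working it through.** The protocol gives no event calculation to reproduce. The check is a comparison of sections, followed by simple expected counts.

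**Step 1. Is there a data source for 3.1(a)?**

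| Place in protocol | What it provides | Post-procedure adverse events? |
|---|---|---|
| 4.4 | History, diet, anthropometry, EGG | No |
| 4.5 | Water volume; symptom scores before and after water | Test-day symptoms only |
| 4.7 | EGG signal analysis; low-volume threshold | No |
| 5 | EGG diagnosis, water volume, test symptoms | No |
| 1.3, Table 1 item 4 | Scores for minor and major complications and re-intervention | Background only; grades undefined; not adopted |

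Section 4.4 is not a closed list, because water volume and symptom scores are collected without appearing in it. The conclusion therefore rests on all these sections together.

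**Step 2. Can the test-day scores serve as the outcome?**
- Timing: sections 4.1 and 4.3 place the first post-procedure assessment at one month, and section 5 tabulates at 3 and 6 months. Section 1.3 places balloon vomiting and pain in week 1 and up to week 3, before any of these.
- Content: the pre-water score at a follow-up visit would show nausea or discomfort present that day. It does not record vomiting, admission, balloon removal or re-intervention.
- Role: section 1.3 proposes the symptoms elicited by the water load test as predictors. Using them as the outcome as well would blur predictor and outcome.

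**Step 3. How much depends on the missing definition?**

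Inputs: n = 50 per procedure group (section 4.2); rates p from section 1.3. Expected count = n × p; chance of no event = (1 − p)^n.

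| What is counted | p | Expected in 50 | Chance of none |
|---|---|---|---|
| Severe events after ESG | 0.02 | 50 × 0.02 = 1 | 0.98^50 = 0.364 |
| Balloon removal | 0.04 | 50 × 0.04 = 2 | 0.96^50 = 0.130 |
| Balloon symptoms up to three weeks | 0.18 | 50 × 0.18 = 9 | below 0.001 |
| Balloon vomiting or pain, week 1 | 0.70 to 0.90 | 50 × 0.70 = 35 to 50 × 0.90 = 45 | effectively 0 |

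The third row takes the 18% as a share of all balloon patients. If it is a share of those with first-week symptoms, the count is 0.18 × 35 = 6.3 to 0.18 × 45 = 8.1. The protocol gives no adverse-event rates for the two surgical groups.

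At one end there is about one event in a group, with roughly a one-in-three chance of none, so prediction could not be examined. At the other end nearly every balloon patient has the event.

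**The case against.** Three points can be made for the protocol.

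- **Something relevant is collected.** The pre-water symptom score at follow-up is a real measure of how patients feel after the procedure, not only a reaction to the water. That stands, but it misses the early weeks and all discrete events.
- **A grading scheme exists.** Table 1 item 4 covers complications and re-intervention. That also stands and makes the repair easier. It is not a cure, because the item is not adopted and neither grade is defined.
- **The study is prospective, with assessments at 1, 3, 6 and 12 months, so sites may well record events.** They may, but nothing in the text available asks them to. The part of section 7 that allots tasks to the team was not available for this check, which leaves some uncertainty.

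A reader might also infer more than the documents support:

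- That events would be found only in hospital charts, with detection differing between an outpatient balloon and inpatient surgery. The protocol states no care setting for any procedure and does not plan retrospective chart capture.
- That only removals and severe events would be charted, leaving about 3 events (2 + 1) in 100 endoscopic patients against 35 to 45. Nothing supports the assumption that no milder event is charted. Section 1.3 also calls the balloon symptoms intolerance, so counting them all as adverse events is itself a choice.

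**Conclusion.** The point holds in this form: adverse events are named in the primary objective and the hypothesis, but no available section defines them or provides for their collection. Followed as written, 3.1(a) has no outcome data.

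The expected count per group runs from about 1 or 2 to 35–45, depending on what is counted and captured. These counts assume that the background rates apply to the study's patients and that each group reaches 50. They show why a definition is needed; the finding itself does not depend on them. It should be corrected before recruitment because the loss cannot be repaired at analysis. Confidence is moderate, given the part of section 7 that could not be checked.

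**What to change.** Add an adverse-event block to section 4.4, defined and collected identically in all four procedure groups and at both hospitals:

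- **Content:** type of event, onset date, end date, minor or major grade, and repeat endoscopy or surgery (following Table 1 item 4, with the two grades defined), plus admission and device removal.
- **Window:** state the period over which events count, from the procedure to the end of follow-up.
- **Collection:** a fixed checklist at the existing 1-, 3-, 6- and 12-month assessments, and a short patient symptom diary for the first weeks.
- **Use:** name this record in 3.1(a) as the outcome, and say whether early balloon intolerance counts as an adverse event or is reported separately.

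Cost: one case-report-form page and a brief diary. The diary is a modest but real burden on up to 200 patients (4 × 50) and on site staff, who must issue, collect and enter it. No added visit or procedure is needed.

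### Adverse events are a primary outcome, but the protocol specifies no collection, definition, grade or time window for them

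*Protocol*

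**What the plan says.** Section 3.1 states, as part of the primary objective, "Pre-intervention EGG parameters and/or changes in EGG parameters after the bariatric intervention can predict adverse events at the end of follow-up". The working hypothesis in Section 2 likewise asks whether "Pre-intervention EGG can predict clinical success and adverse events after bariatric interventions".

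Section 4.4, which sets out the data and variables, has three entries:
- medical history: "history of obesity, evolution of weight, associated comorbidities, personal and family history. Dietary history"
- body measurements: "Anthropometric data: Weight, size, waist circumference, BMI"
- EGG: "Electrogastrography data: clinical diagnosis, percentage distribution, ratios"

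Section 4.5 and the text that follows it add the volume of water drunk and visual analogue symptom scores, taken before the recording and at 10, 20 and 30 minutes after the water. Section 5 covers EGG diagnosis, water volume, water-load symptoms, group comparisons, correlations and a possible logistic regression. It does not name adverse events.

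Severity appears only in the introduction. Item 4 of Table 1 (the BAROS scale adapted to bariatric endoscopy) deducts points for minor complications, major complications and repeat endoscopy or surgery. Minor and major are not defined. The protocol adopts only Part 1 of that scale, excess weight loss, to define failure at 6 months. Section 1.3 also gives background rates: for the balloon, "patients present intolerance such vomit and abdominal pain in 70-90% of cases at the first week", with 18% having symptoms for up to three weeks and 4% having the balloon removed; for ESG, "with rate of severe adverse events around 2" per cent.

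**The concern.** A prospective study has to record its primary outcome as events occur. Clinical success has at least a planned measurement (weight) and a stated failure threshold. Adverse events have neither a planned record nor a threshold.

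If the protocol is followed literally, two hospitals in different countries would each rely on whatever their routine notes contain, with no shared definition. An analysis plan can say how recorded events are to be analysed, but it cannot supply events that nobody was asked to record. If the definition is chosen after the data are seen, the choice among very different event sets also becomes a choice of result.

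**Working it through.** The protocol gives no event count, power or effect size for this objective, so there is no stated figure to reproduce. The check has three parts.

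**1. Objective against data items.**

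| Needed for the adverse-event objective | Where it is specified |
|---|---|
| That events are recorded | Not in 4.4, 4.5, 4.7 or 5 |
| What counts as an event | Not specified |
| Grade | Minor and major in Table 1 only; undefined and not made a study variable |
| Window | End of follow-up (3.1); no start and no ascertainment schedule |
| Analysis | Not named in 5 |

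The water-load symptom scores do not fill the gap. They measure how the patient feels within 30 minutes of drinking water, not complications of the bariatric procedure.

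**2. How far the outcome depends on its definition.** Inputs: 50 patients per procedure (Section 4.2) and the background rates in Section 1.3, read as proportions of all patients treated. Expected events are n × p; the chance of no event is (1 − p)^n.

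| Event | p | 50 × p | Chance of none |
|---|---|---|---|
| Balloon, first-week intolerance | 0.70 to 0.90 | 35 to 45 | about 0 |
| Balloon, symptoms up to three weeks | 0.18 | 9 | below 0.0001 |
| Balloon, removal | 0.04 | 2 | 0.96^50 = 0.13 |
| ESG, severe event | 0.02 | 1 | 0.98^50 = 0.36 |
| Surgical sleeve, RYGB | not given | – | – |

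If the 18% refers only to patients with first-week intolerance, the 9 becomes 0.18 × 35 = 6.3 to 0.18 × 45 = 8.1. The conclusion does not change. Within the balloon group alone, the outcome has between 2 and 45 expected events, depending on which unstated definition is used. At the low end there is too little to relate to any EGG parameter.

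**3. Timing.** Sections 4.1 and 4.3 place the post-procedure assessments at one, three, six and 12 months. The balloon symptoms that Section 1.3 describes occur in the first week and last up to three weeks, so they are over before the first planned contact. Unless the window is stated to start at the procedure, the commonest events the protocol cites could be missed or depend on recall. A change in EGG first measured at one month also cannot predict an event that has already happened.

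**The case against.** The strongest reply is that Section 4.4 is not a complete list. It also leaves out water volume and symptom scores, which the protocol clearly collects elsewhere, so absence from 4.4 alone does not show that events go unrecorded. The available text has no Section 4.6, part of Section 7 is not shown, and sites will probably note complications in routine records. This stands to the extent that the accurate statement is that no collection is specified in the text at hand, not that the objective can never be answered. It does not remove the point: water volume and symptoms have their own collection instructions, and adverse events have none.

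A second reply is that definitions and stratification can be left to the analysis plan. That is fair for the analysis, and Section 5 leaves room for group comparisons and a regression that could include procedure. It is not fair for the recording of a primary outcome.

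Two stronger readings are tempting but unsupported.

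First, a reader might set 70–90% for the balloon beside 2% for ESG and infer that a pooled adverse-event outcome would mostly identify the procedure, so that any EGG difference between groups would pass for prediction. The two rates are of different grades: any first-week vomiting or pain against severe events only. The protocol gives no any-grade rate for ESG and no EGG abnormality rate by procedure, and it does not state a pooled analysis.

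Second, a reader might infer one or two severe events in every group. The figures cover ESG severe events and balloon removal only; nothing is given for the two surgical groups, which are half of the 200 patients.

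**Conclusion.** The concern holds as a mismatch between a primary objective and the planned data. The protocol text specifies no collection, definition, grade or window for an outcome named in both the hypothesis and the primary objective.

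This rests on the text available and on reading the water-load symptom scores as test responses. The counts rest on the protocol's own background rates applied to 50 patients. They show that the definition decides whether the outcome is common or almost absent; they are not forecasts for the surgical groups.

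The mismatch should be corrected. In an observational pilot it does not undermine the rest of the study, but the lost information could not be fully recovered once follow-up has passed.

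**What to change.** - Add procedure-related adverse events to Section 4.4, recorded from the day of the procedure, with the first weeks explicitly included, to 12 months.
- Grade them as minor or major. Item 4 of Table 1 is a possible starting point, but it leaves both terms undefined and is adapted to endoscopy, so the definitions must be written to cover the surgical sleeve and RYGB groups as well.
- Name one graded event, with its window, as the outcome for the adverse-event objective. If post-procedure EGG change is used as a predictor, count only events after that recording.
- Report the outcome by procedure, because event types and rates may differ.
- State that severe events will only be described where few are expected.

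The cost is one form page, a few lines of protocol text, and some means of capturing events before the one-month visit. The price in claims is a more modest statement about severe events.
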